17 RECORDING AND COLLECTION OF DATA

17.1 Electronic Case Report Form (eCRF)

The PI or designee will record all data collected (either written or electronic record of data). Written or electronic data of record must be entered into the eCRF provided for that purpose. In some instances, no prior written or electronic record of data may exist, and data recorded directly into the eCRF is considered source data. The site will be suitably trained on the use of the eCRF and appropriate site personnel will be authorized to provide electronic signatures. The PI is responsible to verify the integrity of the data and acknowledge as such by signature.

All site entries will be made in a secured eCRF and the PI will review the record for completeness. If corrections are necessary to the eCRFs, the PI or designee will update the eCRF and provide documentation for the reason for change.

Completed eCRFs will be submitted according to provided instructions and reviewed by the Coordinating Center to determine their acceptability. If necessary, data correction requests will be generated for resolution by the study site.

17.2 Study Files and Source Documents

Subject confidentiality is strictly held in trust by the participating investigators, research staff, and the Coordinating Center and/or sponsoring institution and their agents. This confidentiality is extended to cover testing of biological samples and genetic tests in addition to the clinical information relating to subjects.

The study protocol, documentation, data and all other information generated will be held in strict confidence. No information concerning the study, or the data will be released to any unauthorized third party, without prior written approval of the sponsoring institution. Authorized representatives of the sponsoring institution may inspect all documents and records required to be maintained by the investigator, including but not limited to, medical records (office, clinic or hospital) and pharmacy records for the subjects in this study. The clinical study site will permit access to such records. Any data, specimens, forms, reports, video/audio recordings, and other records that leave the site will be identified only by a subject identification number (Subject ID, PID) to maintain confidentiality. All records will be kept in a locked file cabinet. All computer entry and networking programs will be done using PIDs only. Information will not be released without written permission of the Subject, except as necessary for monitoring by the Institutional Review Board (IRB), the FDA, and the Office for Human Research Protections (OHRP).

Information about study subjects will be kept confidential and managed according to the requirements of the Health Insurance Portability and Accountability Act (HIPAA) of 1996. Those regulations require a signed Subject HIPAA Authorization informing the Subject of the following:

- What protected health information (PHI) will be collected from subjects in this study
- Who will have access to that information and why
- Who will use or disclose that information
- The rights of a research subject to revoke their authorization for use of their PHI

In the event that a subject revokes authorization to collect or use PHI, the investigator, by regulation, retains the ability to use all information collected prior to the revocation of subject authorization. Each site PI, under the guidance of his/her IRB, is responsible for ensuring that all applicable HIPAA regulations and State laws are met.

18 ETHICS AND REGULATORY CONSIDERATIONS

18.1 Good Clinical Practice

This study will be conducted in compliance with the protocol and accordance with Good Clinical Practice (GCP) guidelines, as defined by the International Conference on Harmonization (ICH)

Guideline, Topic E6, the United States Code of Federal Regulations (CFR), Title 21, Part 50 – Protection of Human Subjects, and Part 56 – IRBs, HHS Regulations (45 CFR part 46, 160, 164 HHS Regulations for the Protection of Human Subjects; HIPAA; 42 CFR part 50), Subpart F HHS Regulations for Responsibility of Applicants for Promoting Objectivity in Research for Which PHS Funding Is Sought HIPAA, State and Federal regulations and all other applicable local regulatory requirements and laws.

Study personnel involved in conducting this study will be qualified by education, training and experience to perform their respective task(s) in accordance with GCP.

No study document shall be destroyed without prior written agreement between the Coordinating Center and the investigator. Should the investigator wish to assign study records to another party or move them to another location, he/she may do so only with the prior written consent of the Coordinating Center.

18.2 Institutional Review Board (IRB)

Institutional Review Boards must be constituted, and their authority delegated through the institution's normal process of governance according to applicable State and Federal requirements for each participating location. Each participating institution must provide for the review and approval of this protocol and the associated informed consent documents and recruitment material by an appropriate IRB registered with the OHRP. Any amendments to the protocol or consent materials must also be approved before they are placed into use. In the United States, only institutions holding a current US Federal wide Assurance (FWA) issued by OHRP may participate. Refer to: <http://www.hhs.gov/ohrp/assurances/>.

The investigator must obtain approval from the IRB for all subsequent protocol amendments and, when warranted, changes to the informed consent document. Protocol and informed consent form amendments can be made only with the prior approval of the Coordinating Center. The investigator may not implement any protocol deviation without prior notification, review, and documented approval by the Study Director, except where necessary to eliminate an immediate hazard to study subjects, or when change(s) involve only logistical or administrative aspects of the trial. The investigator shall notify the IRB of deviations from the protocol or serious adverse events occurring at the site, in accordance with local procedures.

18.3 Informed Consent and Health Insurance and Portability and Accountability Act (HIPAA) Compliance

Informed consent will be obtained in accordance with 21CFR §50.25, and ICH Good Clinical Practice. Applicable HIPAA privacy notifications will be implemented, and HIPAA authorizations signed before protocol procedures are carried out. Information should be given in both oral and written form as deemed appropriate by the Site's IRB.

Prior to the beginning of the trial, the investigator must obtain the IRB's written approval of the informed consent form and any other written information to be provided to subjects and be acceptable by Regulatory Affairs. Consent forms must be in a language fully comprehensible to the prospective subjects and/or their authorized representatives and study partners. Subjects, their relatives, guardians, or authorized representatives and study partners will be given ample opportunity to inquire about the details of the study. Prior to a subject's participation in the trial, the written informed consent form should be signed and personally dated by the subject or by the subject's legally acceptable representative, and by the person who conducted the informed consent discussion. Subjects will be provided a copy of the signed ICF.

The informed consent will not only cover consent for the trial itself, but for the genetic samples/data/storage and biomarker samples/data/storage as well. Consent forms will specify that DNA and biomarker samples are for research purposes only; the tests on the DNA and biomarker samples are not diagnostic in nature and subjects will never receive results.

19 STUDY MONITORING

The clinical monitor is responsible for inspecting the case report forms (CRFs) and source documentation at specific time points throughout the study to verify adherence to the protocol, completeness and accuracy of the data, and adherence to local regulations on the conduct of clinical research. The monitoring visits must be conducted according to the applicable ICH and FDA guidelines to ensure protocol adherence, quality of data, drug accountability, compliance with regulatory requirements and continued adequacy of the investigational site and its facilities. The Site Investigator will cooperate in the monitoring process by ensuring the availability of the CRFs, source documents and other necessary documents at the time of the monitoring visits. Site Investigator will promptly address any matters brought to his/her attention by the monitor. The Site Investigator may also be asked to meet in-person with the site monitor during certain visits.

20 AUDIT

In accordance with ICH E6 (Good Clinical Practices) representatives of the Coordinating Center and/or Sponsor and/or regulatory agency may select this study for audit. The investigator and study staff are responsible for maintaining the site master file containing all study-related regulatory documentation as outlined by Regulatory Affairs that will be suitable for inspection at any time by the CRO, Sponsor, its designees, and/or regulatory agencies. Inspection of site facilities (e.g., pharmacy, laboratories) to evaluate the trial conduct and compliance with the protocol may also occur.

21 RECORD RETENTION

Essential documents and study records must be retained for a minimum of seven years following primary publication of study results. The Coordinating Center will notify sites when retention of such documents is no longer required. Essential documents should be retained for at least 2 years

after the last approval of a marketing application in an ICH region and until there are no pending or contemplated marketing applications in an ICH region or at least 2 years have elapsed since the formal discontinuation of clinical development of the investigational product. These documents should be retained for a longer period however if required by the applicable regulatory requirements or by an agreement with the Sponsor. It is the responsibility of the Sponsor to inform the investigator/institution as to when these documents no longer need to be retained.

23 APPENDIX 1: SCHEDULE OF EVENTS

Visit Timing ^a	Day -42 to 0		Day 14 (± 4)	1-3 days prior to confinement	Days 25 (± 2)		
Procedures	Screening	Baseline	Phone	Pre- Confinement Phone Contact	Confinement		
					Admission	6-Hour Sampling	Discharge ^e
Informed Consent	X						
Demographics	X						
Medical and Psychiatric History	X						
Height and BMI	X						
Inclusion and Exclusion Criteria	X	X					
Urine Dipstick Pregnancy Test	X						
Physical and Neurological Examination	X	X			X		X
AD & PD: MMSE	X	X			X		
AD: CDR	X	X			X		
AD: ADAS-Cog 14		X			X		
AD & PD: WAIS-IV		X			X		
PD: MDS-UPDRS	X ^g	X			X		
C-SSRS	X	X			X		
Vital Signs ^b	X	X			X	X	X
Clinical Lab Safety Tests	X	X ⁱ			X ⁱ		
12-Lead ECG	X	X			X		X
MRI of Brain ^c	X						
Adverse Events	X	X	X	X	X	X	X
Prior/Concomitant Medication	X	X	X	X	X	X	X
Randomization		X					
Dispense Study Drug		X					

Dosing Study Drug in Clinic		X				X	
Study Drug Compliance Check			X	X	X		
APOE Genotype and DNA Markers		X					
Blood Sampling for PK		X				X	
Lumbar Puncture for baseline Pharmacodynamics		X					
LP Catheter Placement ^h					X		
Sampling for Biomarkers in Blood, Plasma and CSF		X				X ^f	
24-Hour Phone Follow-Up ^d		X					X
Lumbar Xray ^h (Optional)	X						

^a Refer to Section 9 for more details on visit timing and windows.

^b Vital signs will include sitting blood pressure, pulse, temperature, respiration rate, and weight, except during the 6-hour Sampling Phase of the Confinement Visit when weight will not be included.

^c An MRI of the brain will only be conducted if there is no brain MRI available from within the window specified in Inclusion Criteria.

^d Phone Follow-up should occur approximately 24-hours after completion of the LP procedure at Baseline and after discharge from the Confinement Visit.

^e The Early Discontinuation Visit will contain the same assessments as the Pre-confinement Visit.

^f Sampling Times: 0,1,2,3,4,5,6 hrs (± 10 mins for collection)

^g Hoehn & Yahr Stage only for inclusion determination

^h X-Ray is only required if LP insertion will not be performed with fluoroscopy

ⁱ Safety labs at baseline and confinement (for sample 0 hour) should be taken fasted

24

APPENDIX 2: SEVERITY EVALUATION OF CHOLINERGIC ADVERSE EVENTS (ADVERSE EVENTS OF SPECIAL INTEREST)

Because of the potential of additive cholinergic adverse events caused by a combination of Posiphen and cholinesterase inhibitors in some subjects the severity of such adverse events should be carefully evaluated taking the criteria below into consideration (modified from “CTCAE version 4.03.)

Adverse Event	Mild	Moderate	Severe
nausea	Loss of appetite without alteration in eating habits	Oral intake decreased without significant weight loss, dehydration or malnutrition	Inadequate oral caloric or fluid intake; tube feeding, TPN, or hospitalization indicated
vomiting	1 - 2 episodes (separated by 5 minutes) in 24 hrs	3 - 5 episodes (separated by 5 minutes) in 24 hrs	≥ 6 episodes (separated by 5 minutes) in 24 hrs; tube feeding, TPN or hospitalization indicated
diarrhea	Increase of <4 stools per day over baseline	Increase of 4 - 6 stools per day over baseline	Increase of ≥ 7 stools per day over baseline; incontinence; hospitalization indicated; limiting self-care ADL
anorexia	Loss of appetite without alteration in eating habits	Oral intake altered without significant weight loss or malnutrition; oral nutritional supplements indicated	Associated with significant weight loss or malnutrition (e.g., inadequate oral caloric and/or fluid intake); tube feeding or TPN indicated
fatigue	Fatigue relieved by rest	Fatigue not relieved by rest; limiting instrumental ADL	Fatigue not relieved by rest, limiting self-care ADL

1 Final	26/02/2021	[name] [name]	Section 6.1 – 6.4.1 updated; Section 7 analysis table schedule added; Sections 7.2.1, 7.2.2, 7.2.3 and 7.4 updated throughout. Text updated following Sponsor's comments dated 8 February 2021 and plot templates added (Appendix 2) and references to plot templates included within the SAP.

CONTENTS.

1. INTRODUCTION.	4
2. OBJECTIVES.	4
3. STUDY DESIGN.	6
4. POPULATION	8
5. STUDY METHODS	8
6. STATISTICAL METHODS.	17
7. PRESENTATION.	20
8. REFERENCES.	28
9. FINALISATION OF STATISTICAL ANALYSIS PLAN.	28
Appendix 1	Table Shells (Parts 1 & 2)
Appendix 2	Plot Templates (Parts 1 & 2)
Appendix 3	Listings shells (Parts 1 & 2)

1. Introduction.

Progressive neurodegenerative diseases such as Alzheimer's (AD) and Parkinson's disease (PD) share many common characteristics, including the central role of neurotoxic aggregating proteins in their pathogenesis.

Posiphen has been shown to reduce the levels of several neurotoxic aggregating proteins that contribute to the progression of AD and PD. The aim of this study is to assess the potential effects of posiphen in patients with AD and PD in the assessment of target and pathway engagement in CSF and plasma. Collectively, these endpoints will help assess efficacy and add valuable information to the Posiphen clinical development programme.

The purpose of this Statistical Analysis Plan (SAP) is to describe the planned analyses and presentations of data collected from the three 'patient cohorts'. The findings will then be interpreted in four statistical reports which will include tables, figures and lists (TFLs) based on this SAP and to support the subsequent production of the Clinical Study Report (CSR).

This statistical analysis plan is based on protocol: ANVS-12003_AD-PD-CSFProtocol_v3_8-21-2020 and will be finalised before the first cohort complete Part 1 and are unblinded for analysis.

From a scheduling perspective, four separate analyses will be performed. The first once the first cohort of 14 PD patients have completed Part 1 and the second once the second cohort of 14 AD patients complete Part 1. The third analysis will be carried out when the third cohort (4 treatment groups) in Part 2 has completed all assessments but this will also include the Placebo and 80mg posiphen patients from the Part 1 PD cohort. The fourth analysis will include the pharmacokinetic data from both Part 1 (AD and PD patients) and Part 2 (PD patients), and, if required, a presentation of the results from the evaluation of infective particles in CSF and exosomes in plasma.

Given the study design (patient type and treatment dose) all safety evaluations will be reported separately in each of the first three analyses.

The following study documents were used for the preparation of this SAP:

- ANVS-12003_AD-PD-CSFProtocol_v3_8-21-2020 (protocol)
- ANVS 12003 (Annov 251151) SDTM 3.2 Annotated CRF v0.4 20200902

The example layouts of the data presentations are shown in Appendices 1-3 for tables, figures and listings, respectively.

2. Objectives.

A broad range of objectives are specified in this early stage exploratory investigation. They include safety and tolerability in both patient groups (AD and PD). Pharmacodynamics and early Efficacy indicators with biomarker target engagement, pathway engagement and functional/cognitive measures respectively across both Part 1 and 2 of the study.

Drug pharmacokinetics in CSF and blood will also be characterised at the dose selected in AD and PD patients in Part 1 and across the range of doses selected in PD patients in Part 2.

Part 1 - Safety, tolerability, pharmacodynamics, efficacy and pharmacokinetics of posiphen (80mg QD after 25 days) in early AD and PD patients.

Part 2 - Safety, tolerability, pharmacodynamics, efficacy and pharmacokinetics of posiphen (5, 10, 20, 40mg QD after 25 days) in early PD patients.

The primary comparisons of interest performed in Part 1 and Part 2 are the changes from baseline (Within treatment group). The null hypothesis throughout is that there is no difference between the Day 25 end of treatment and Pre-treatment baseline ($H_0. X_{end}=X_{base}$, $H_1. X_{end} \neq X_{base}$).

Between treatment group comparisons will also be done (but are of secondary interest due to the small sample size). Here, the null hypothesis is that there is no difference between any of the treatment groups at the end of treatment ($H_0. Placebo=X_{5mg}=X_{10mg}=X_{20mg}=X_{40mg}=X_{80mg}$, $H_1. Placebo \neq X_{5mg} \neq X_{10mg} \neq X_{20mg} \neq X_{40mg} \neq X_{80mg}$).

2.1 Endpoints

2.1.1 Pharmacodynamics

Pharmacodynamic effects are based on target engagement outcome measures with the levels of neurotoxic proteins measured in plasma and CSF. Potential drug efficacy is assessed through pathway engagement measurements of the levels of proteins obtained in blood, plasma and CSF.

2.1.1.1 Target Engagement

Levels of neurotoxic proteins measured in plasma and CSF are:

- aSYN monomers
- A β monomers: A β 40, A β 42
- soluble Amyloid Precursor Proteins: sAPP α and sAPP β
- T-tau and P-tau protein

2.1.1.2 Pathway Engagement

Levels of proteins involved in the toxic cascade and measured in plasma and CSF are:

- Axonal transport
- Inflammatory factors
- Synaptic factors
- Control proteins

Plus:

Infective particles (oligomers) in CSF
and
Exosomes from platelet-poor plasma

2.1.2 Efficacy (Functional/Cognitive)

Although clinical benefit is not expected within this early phase, exploratory investigation, the AD and PD specific tests performed will provide valuable information on likely estimates of

variability for use in future power calculations to support sample sizes for posiphen efficacy clinical trials.

For both AD and PD patients, the Mini-Mental State Examination (MMSE) will be used as a global measure of cognition and the Coding subtest from the Weschler Adult Intelligence Scales, 4th edition (WAIS-IV) will be used as a sensitive measure of CNS dysfunction.

AD patients will undertake the Alzheimer's disease Assessment Scale-cognitive subscale (ADAS-Cog 14) and functional impairment will be evaluated using the Clinical Dementia Rating (CDR) scale.

PD patients will undertake the MDS-Unified Parkinson's disease rating scale (MDS-UPDRS) to assess the non-motor and motor experiences of daily living.

2.1.3 Safety and Tolerability

Safety assessments for both parts of the study are based on physical examinations, clinical laboratory data, vital signs (blood pressure and heart rate), adverse events (AEs) and serious AEs [SAEs], ECGs (12 lead) and the Columbia suicide rating scale (C-SSRS). Adverse events are assessed throughout but all other assessments are to be made at entry (Baseline) and on the Day 25 final assessment day.

2.1.4 Pharmacokinetics

PK parameters of the parent drug, posiphen, will be determined for both AD and PD patients at 80mg QD dose group after 25 days of repeated dosing (Part 1) and for PD patients at 5, 10, 20, 40mg QD after 25 days of repeated dosing for PD patients (Part 2).

Specific parameters of interest are Area under the curve (AUC 0-t, 0-inf), maximum concentration (Cmax), time of maximum concentration (Tmax), half-life (t_{1/2}), and clearance (CL).

3. Study Design.

This study will be conducted in two parts: Part 1 will evaluate the safety, tolerability, and pharmacokinetics of Posiphen in 14 Early AD and 14 Early PD patients at 80 mg QD.

Each group will include 14 Early AD patients, randomly assigned, 10 to posiphen and 4 to placebo and 14 Early PD patients randomly assigned, 10 to Posiphen and 4 to placebo.

Part 1 will also include exploratory measures of pharmacodynamics and efficacy of Posiphen with target engagement, pathway engagement and functional/cognitive measures, including the degree of memory loss and cognitive function in AD patients as well as the degree of motor impairment and non-motor symptoms and quality of life in PD patients.

Part 2 will evaluate the safety, tolerability, and pharmacokinetics of posiphen in 40 patients with early PD, who will be randomly assigned to each of 4 dose levels; 5 mg QD, 10 mg QD, 20 mg QD and 40 mg QD.

Part 2 will also include exploratory measures of pharmacodynamics and efficacy of posiphen in Early PD patients with target engagement, pathway engagement and functional/cognitive measures, including the degree of motor impairment as well as other non-motor symptoms and quality of life in PD patients.

Full clinical details are given in the protocol.

3.1 Power and Sample Size Determination

This is an exploratory investigation of safety, tolerability, pharmacokinetics, pharmacodynamics and efficacy focusing on target engagement, pathway engagement and functional/cognitive measures. Ten patients per dose group will provide sufficient data to demonstrate within group changes for sAPP α and sAPP β to be of the order of 20-40% (see Table 1 below) and to characterise the PK of posiphen and support potential dose proportionality analyses.

Table 1: Sample Size Estimation

Biomarker	SD	Delta effect size	Within treatment group change	N/Group*
sAPP α	0.1695	0.3 to 2 SD	36%	9
sAPP β	0.1695	0.3 to 2 SD	24%	9

*With 80% power and 0.05 two tailed significance level

NB. Alpha-synuclein (aSYN) and in neurotransmitters provide valuable supporting information but changes are anticipated to be smaller and would require larger group sizes.

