6.2 Power and Sample Size Determination

This is an exploratory study to assess safety, tolerability and pharmacokinetics for Early AD and Early PD patients in addition to investigating pharmacodynamics and efficacy focusing on target engagement, pathway engagement and functional/cognitive measures. 10 patients per dose group provides enough data to characterize the PK of Posiphen as well as adequately supporting potential dose proportionality analyses.

Due to the sample size computation below, we will state that sAPP α , sAPP β and aSYN were given specific consideration in deciding the need to have 10 Posiphen patients in each treatment group given their specific importance in the emergence and progression of AD and PD. The statistical background and rational for having 10 Posiphen patients in each treatment group to have a meaningful interpretation of sAPP α , sAPP β and aSYN data are outlined below.

The statistical evaluation of our previous study in MCI patients with soluble APP α and β levels measured in spinal fluid before and after Posiphen administration (Protocol QR12001) can be used to power this study ([name] 2012). All assay data collected were analyzed using a repeated measure mixed model analysis of variance. The model included Day (Day 11/Day0) as a fixed effect, Time (9 time points per person between 0 and 6 hours) as a repeat measure effect

and Patient (18 samples per person total) as a random effect. Data are presented as means \pm SEs. The statistical evaluations were undertaken by Data Magik (Salisbury, UK).

Human biomarker	CSF % of time 0	SE	p Value
(A) AD biomarkers			
sAPP α	-59.9%	0.231	0.0006
	-34.1%	0.659	0.0661
sAPP β	-57.7%	0.361	0.0001
	-34.0%	1.516	0.0901

Analysis of sAPP α and β using type, day and id as variables shows:

	type	time	N	delta_MN	delta_SE	delta_SD	%chng_MN	%chng_SE	z	pv
1	alpha	1.5h	4.0000	0.0603	0.0960	0.1921	0.0561	0.2167	0.6273	0.5304
2	alpha	2h	4.0000	0.1245	0.0423	0.0846	0.3020	0.0690	2.9445	0.0032
3	alpha	6h	3.0000	0.2660	0.0558	0.0967	0.4542	0.1367	4.7650	0.0000
4	alpha	8h	4.0000	0.3135	0.0847	0.1695	0.5248	0.0653	3.6995	0.0002
5	alpha	0h	4.0000	0.0948	0.0928	0.1856	0.1691	0.2493	1.0213	0.3071
6	alpha	12h	4.0000	0.2960	0.0623	0.1245	0.4966	0.0862	4.7549	0.0000
7	alpha	1h	4.0000	-0.0683	0.1660	0.3320	-0.4285	0.6604	-0.4111	0.6810
8	alpha	3h	4.0000	0.4858	0.3922	0.7844	0.3579	0.1981	1.2385	0.2155
9	alpha	4h	4.0000	0.3030	0.2753	0.5505	0.3200	0.2905	1.1008	0.2710

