10	beta	1.5h	4.0000	-0.1160	0.2670	0.5339	-0.7568	0.9151	-0.4345	0.6639
11	beta	2h	4.0000	0.1975	0.0876	0.1752	0.3639	0.1315	2.2550	0.0241
12	beta	6h	3.0000	0.4717	0.0572	0.0991	0.5910	0.0519	8.2431	0.0000
13	beta	8h	4.0000	0.5715	0.1271	0.2542	0.6648	0.0550	4.4960	0.0000
14	beta	0h	4.0000	0.1092	0.1134	0.2268	0.1425	0.2227	0.9632	0.3354
15	beta	12h	4.0000	0.4620	0.0581	0.1161	0.6040	0.0604	7.9570	0.0000
16	beta	1h	4.0000	-0.4895	0.1652	0.3304	-1.4024	0.6361	-2.9635	0.0030
17	beta	3h	4.0000	2.2147	1.9988	3.9977	0.5025	0.1616	1.1080	0.2679
18	beta	4h	4.0000	0.0277	0.3313	0.6626	-0.2181	0.2404	0.0838	0.9332

The results of the 10 days at 8 hours on sAPP α and β is SD = 0.1695.

Assuming type one error, $\alpha=0.05$ and type two error, $\beta=0.2$, or a power of 0.8, the calculated sample range of delta effect sizes was 0.3 to 2 SD.

	delta	standardized_delta	N
1	0.08	0.30	175.00
2	0.10	0.40	99.00
3	0.13	0.50	64.00
4	0.15	0.60	45.00
5	0.18	0.70	39.00
6	0.20	0.80	26.00
7	0.23	0.90	20.00
8	0.25	1.00	17.00
9	0.28	1.10	14.00
10	0.31	1.20	12.00
11	0.33	1.30	10.00
12	0.36	1.40	9.00
13	0.38	1.50	8.00
14	0.41	1.60	7.00
15	0.43	1.70	7.00
16	0.46	1.80	6.00
17	0.48	1.90	5.00
18	0.51	2.00	5.00

sAPP α

Using the above data, we can calculate that a power analysis of APP α shows the requirement of 9 people to see a 36% change in sAPP α levels at a statistical significance level of >0.05

delta	standardized_delta	N
1	0.05	175.00
2	0.07	99.00
3	0.08	64.00
4	0.10	45.00
5	0.12	33.00
6	0.14	26.00
7	0.15	20.00
8	0.17	17.00
9	0.19	14.00
10	0.20	12.00
11	0.22	10.00
12	0.24	9.00
13	0.25	8.00
14	0.27	7.00
15	0.29	7.00
16	0.31	6.00
17	0.32	5.00
18	0.34	5.00

sAPP β

Using the above data, we can calculate that a power analysis of APP β shows the requirement of 9 people to see a 24% change in sAPP β levels at a statistical significance level of >0.05 . We are expecting changes in sAPP α and β levels to be between 20 and 50% and for the higher doses an $n < 5$ would be adequate to detect those changes.

aSYN

However, we do not expect the changes in alpha-synuclein and in neurotransmitters to be that pronounced. Therefore, we chose an $n=10$. If dropouts are to occur, they will be replaced to allow the full sample size of 5×10 participants to be achieved.

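### The sAPP power claim behind ten patients per group does not follow from the pilot data: SDs are swapped, raw units are read as percent, and the time point is not the one tested

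*SAP*

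**What the plan says.** SAP 3.1 says that "Ten patients per dose group will provide sufficient data to demonstrate within group changes for" sAPPα and sAPPβ in the region of 20–40%. Its Table 1 lists SD 0.1695 for both markers, a within-group change of 36% for sAPPα and 24% for sAPPβ, and N=9 per group for each, at 80% power and two-sided 0.05.

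The source is Protocol 6.2. It tabulates pilot results (Protocol QR12001) by marker and hour, mostly with N=4, with raw differences (delta_MN, delta_SD) and percent changes (%chng_MN, %chng_SE) in separate columns. It takes one SD for both markers, introduced as "The results of the 10 days at 8 hours on" sAPPα and β, and prints two grids of delta against N. From the first it says the analysis "shows the requirement of 9 people to see a 36% change in" sAPPα; from the second, that it "shows the requirement of 9 people to see a 24% change in" sAPPβ. It adds that for the higher doses fewer than 5 patients "would be adequate to detect those changes".

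On alpha-synuclein, the protocol says "we do not expect the changes in alpha-synuclein and in neurotransmitters to be that pronounced. Therefore, we chose an" n of 10. The note under SAP Table 1 says of the same markers that "changes are anticipated to be smaller and would require larger group sizes".

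SAP 6.1 sets the Day 0 to Day 25 test as an ANOVA of percent change from Day 0 pre-dose 0h to Day 25 pre-dose 0h. SAP 5.2.1 has Day 25 sampling from 0 to 6h.

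**The concern.** Table 1 cannot be right as printed: one SD, one alpha and one power cannot give the same N for two different changes. The deltas in the protocol grids also look like multiples of a raw-unit SD, although they are quoted as percentages. The SD comes from an hour that this trial does not sample.

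This is the only numerical power statement in either document, and it covers the within-group comparison that SAP Section 2 calls primary. A reader would conclude that ten patients had been shown to be enough for 20–40% sAPP changes. Part 1 biomarker results also inform which assays continue into Part 2, so it matters whether that sensitivity was established. sAPP is exploratory and the primary outcomes are safety and PK, so the choice of ten patients is not itself in question.

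**Working it through.** **Inputs (Protocol 6.2 pilot table, N=4 in each row)**

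| Row | delta_MN | delta_SD | %chng_MN | %chng_SE |
|---|---|---|---|---|
| sAPPα 8h | 0.3135 | 0.1695 | 0.5248 | 0.0653 |
| sAPPβ 8h | 0.5715 | 0.2542 | 0.6648 | 0.0550 |
| sAPPα 0h | 0.0948 | 0.1856 | 0.1691 | 0.2493 |
| sAPPβ 0h | 0.1092 | 0.2268 | 0.1425 | 0.2227 |

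All sample sizes use the noncentral t, two-sided 0.05, 80% power.

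**1. Reproducing N=9.** The protocol's N column is the two-sample t-test size per group: 0.3 SD gives 175.4 (printed 175), 1.0 SD gives 16.7 (17) and 1.4 SD gives 9.08 (9). One cell of the first grid, 39 at 0.70 SD, departs from the formula and from the second grid (33), with no bearing on N=9. A paired test at 1.4 SD needs 6.18, so 7. Heading this N as a within-group figure is therefore a labelling fault in the conservative direction.

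**2. Which SD built each grid.** Multiply each standardised delta (0.3 to 2.0) by a candidate SD and round to two decimals. The second grid shows no standardised column as read, so the first grid's values were used row by row.

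| Grid | Rows matching 0.2542 (β) | Rows matching 0.1695 (α) |
|---|---|---|
| Used for sAPPα | 18 of 18 | 0 of 18 |
| Used for sAPPβ | 0 of 18 | 18 of 18 |

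The protocol's sentences tie 36% to sAPPα and 24% to sAPPβ, so a misplaced table label does not explain the swap.

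**3. The stated deltas with each marker's own 8h SD**

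- sAPPα: 0.36 / 0.1695 = 2.12 SD. Two-sample n 4.67, so 5; paired 4.01, so 5.
- sAPPβ: 0.24 / 0.2542 = 0.944 SD. Two-sample n 18.6, so 19; paired 10.9, so 11.

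The first line also shows that Table 1's sAPPα row contradicts itself: with its printed SD the answer is 5, not 9.

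**4. Units.** 1.4 × 0.2542 = 0.356 and 1.4 × 0.1695 = 0.237 are raw assay units. They became 36% and 24%. The scales are not interchangeable: for sAPPα at 8h the raw change is 0.3135 and the percent change 52.5%. The sentence about fewer than 5 patients shares these faults: a raw 0.50 needs n of 3.1 with SD 0.1695 but 5.2 with SD 0.2542.

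**5. Time point.** Percent-change SD = %chng_SE × √4.

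- 8h: 0.0653 × 2 = 13.1% (α); 0.0550 × 2 = 11.0% (β).
- 0h: 0.2493 × 2 = 49.9% (α); 0.2227 × 2 = 44.5% (β), about four times larger.

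For n=10 with the 0h SDs, as a paired test or with the residual degrees of freedom of the planned ANOVA (Part 1: 14 − 2 = 12; Part 2: 54 − 6 = 48):

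| Analysis | Detectable d | sAPPα | sAPPβ | Power, 36% α | Power, 24% β |
|---|---|---|---|---|---|
| Paired, 9 df | 0.996 | 49.7% | 44.4% | 0.53 | 0.33 |
| Part 1, 12 df | 0.965 | 48.1% | 43.0% | 0.56 | 0.35 |
| Part 2, 48 df | 0.904 | 45.1% | 40.3% | 0.61 | 0.39 |

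The 95% chi-square intervals for these SDs (3 df) are 28–186% and 25–166%. Carried through the Part 1 row, the detectable change runs from about 27 to 179% (α) and 24 to 160% (β), although a reduction cannot exceed 100%. With the 8h percent-change SDs, power at the stated changes exceeds 99%.

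**6. Pilot hour labels.** The table has 8h and 12h rows, but the protocol's model description gives "9 time points per person between 0 and 6 hours", and Protocol 3.2 also describes 6 hours. The labels need checking before any row is used.

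**The case against.** The strongest reply has four parts.

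**The swap barely touches the headline.** Exchanging the labels gives 0.24 for sAPPα and 0.36 for sAPPβ at N=9, still nominally 24% and 36%. That holds only while raw units are read as percent. Taking delta_MN / %chng_MN as a rough baseline (0.597 and 0.860), the unswapped values are 0.237 / 0.597 ≈ 40% and 0.356 / 0.860 ≈ 41%.

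**The figure of 19 is a two-sample number.** For the within-group test the requirement is 11, and ten patients give about 76% power. That is fair, and for sAPPα the error is conservative (9 stated, 5 needed).

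**The fourfold gap appears only on the percent scale.** The raw 0h SDs (0.1856, 0.2268) are close to the 8h ones. With them, paired power at n=10 for 0.36 and 0.24 is above 99% and about 84%. With rough baselines, detectable changes are about 28–33%, inside 20–40%. This is a real caution against reading the 0h percent figures as proof of low power. But SAP 6.1 analyses percent change, with a log analysis as fallback. The rough baselines are ratios of means, and a log-ratio SD cannot be derived from the documents.

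**The alpha-synuclein note may mean larger than sAPP needs, not larger than ten.** That reading is possible, but the note sits directly beneath the ten-per-group statement and reads naturally as a conflict.

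What stands of the reply is that the 0h magnitudes are weak evidence and that n=10 also rests on PK and safety. The SD, unit and Table 1 faults are untouched.

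**Conclusion.** The concern holds. The 36%, 24% and 20–40% figures do not follow from the cited data: each marker carries the other's SD, raw differences are reported as percentages, and the SD is from an hour other than the planned 0h comparison. Confidence in the grid, unit and label findings is high; they need nothing beyond the two documents.

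Confidence in the 0h magnitudes (detectable change about 45–50% for sAPPα and 40–44% for sAPPβ) is low. They rest on four patients at 4x60 mg/day and assume that:

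- the hour labels are right;
- Day 11 versus Day 0 variability carries over to a once-daily trough;
- SDs are equal across groups;
- sAPP is retained in Part 2;
- normal theory is adequate, although the pilot percent changes look skewed (for sAPPβ at 4h the mean raw delta is +0.0277 while the mean percent change is −0.2181).

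The pilot cannot settle the power in either direction. This should be fixed, but it does not undermine the sample size for the primary outcomes.

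**What to change.** Keep n=10, resting on safety, PK and dose proportionality. In Protocol 6.2 and in SAP 3.1 with Table 1, remove the 36%, 24% and 20–40% figures and the sentence about fewer than 5 patients. Reconcile the protocol's use of alpha-synuclein to justify ten patients with the SAP note that it would need larger groups. Then choose one of two courses:

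- **(a) No sAPP power claim.** For example: *Group size was set at ten for safety, PK and dose proportionality; biomarkers are exploratory and no power is claimed for them.*
- **(b) An illustrative range.** Use each marker's own SD on the analysed scale (percent or log-ratio, pre-dose 0h) for the within-group test. State that it rests on four pilot patients at 4x60 mg/day, that about 45–50% (sAPPα) and 40–44% (sAPPβ) are point estimates only, and that the pilot hour labels were checked.

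The cost is wording only, with no extra patients and no change to the analysis. Under (a) the documents no longer carry a biomarker power claim. Under (b) the stated detectable effects become larger and less certain.
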